6.4.7. Lactation

The effect of CD62L⁻ Tem in lactating females is currently unknown. In pre-clinical studies alemtuzumab was detected in the milk and offspring of lactating female mice. It is unknown whether alemtuzumab is excreted in human milk, and a risk to the suckling newborn/infant cannot be excluded. Therefore, females who are breast feeding are excluded from trial entry.

7. **REGISTRATION PROCEDURES**

There is a two-step registration process for ToTem:

- 1. Trial Registration Initial registration into the trial of the patient and donor prior to donor apheresis and patient transplant conditioning.
- Confirmation of eligibility for trial treatment after patient stem cell transplant and within 2 days prior to CD62L⁻ Tem infusion, patient eligibility for trial treatment should be reassessed (see section 6.2.3) and confirmed with UCL CTC.

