7.1. Trial Registration

Registration will be undertaken centrally at UCL CTC and this must be performed **prior to donor apheresis and patient transplant conditioning**. Pre-registration evaluations for patients and donors should be carried out at sites as detailed in section 9.1 (Pre-Registration Assessments).

Following the pre-registration assessments, confirmation of eligibility, and the consent of the patient and donor at a site, the registration CRF must be fully completed and faxed to UCL CTC. This will be used to confirm patient and donor eligibility. If further information is required UCL CTC will contact the person submitting the registration form to discuss the patient and request updated forms to be faxed.

N.B. If the site is unable to fax, registration forms may be sent by email. If emailing forms, identifiable information on the form (e.g. date of birth) must be redacted before it is emailed to [contact]. The identifiable information must be provided to UCL CTC via telephone so that UCL CTC can transcribe this information onto the form. The un-redacted form must then be posted to UCL CTC, and a copy kept in the patient file at site.

Once eligibility has been confirmed a trial number (e.g. TOT-01) and cohort dose allocation will be assigned to the patient. The donor will also be assigned a trial number (e.g. TOT-01-D) which will link them to the trial patient.

UCL CTC will e-mail confirmation of the patient's inclusion in the trial, their trial number and cohort allocation to the PI, main contact and main research nurse (if different from main contact) and the cell processing laboratory (CCGTT). Details of this should be added to the registration form by the site.

Registration fax number: Registration email address: [name] [contact]

UCL CTC Office hours:

09:00 to 17:00 Monday to Friday, excluding Bank Holidays

Once registration has been completed the **patient and the donor** must be provided with the following:

- A copy of their signed consent form and patient/donor information sheet
- A patient contact card. Site contact details for 24 hour medical care must be added to this card. Patients should be advised to carry this with them at all times while participating in the trial.

After registration the ToTem GP letter **must be sent to the patient's GP** by the site to inform them they are participating in the trial.

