8.2. Treatment Details

8.2.1. Donor CD62L⁻ Tem Apheresis and PBSC/Bone marrow harvest

Following Trial Registration, the donor may undergo single steady state apheresis for the purpose of selecting CD62L⁻ Tem. The trial site must arrange the time and date of leukapheresis with the Centre for Cell, Gene and Tissue Therapeutics (CCGTT) as soon as possible after registration (see **Error! Reference source not found.**)

The preferred schedule is for donors to undergo apheresis between -14 to -7 days prior to day 0 of the stem cell transplant (the day when the stem cells are infused). The apheresis product will then be couriered to CCGTT and processed according to the patient's cohort. Following the steady state apheresis, donors will then undergo peripheral blood stem cell (PBSC) mobilization/harvest or bone marrow harvest according to local policies.

Because of the logistics involved in scheduling apheresis appointments and processing laboratory availability at each trial centre, it will also be permissible for donors to undergo a steady state apheresis after PBSC or bone marrow donation. Therefore, a maximum window for apheresis is allowed between -14 days prior to and up to +24 days following day 0 of the transplant with prior agreement from CCGTT.

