9.5. Assessments during Follow Up

The following investigations should be performed at days +100, +180, +270 and +360 post-stem cell transplant (+/- 10 days):

- Disease assessment as per local policy
- Adverse reaction assessment (including GvHD assessment)
- Physical examination & weight
- Full blood count with differential
- Biochemistry (sodium, potassium, urea, creatinine, calcium, phosphate, albumin, total protein, bilirubin, AST/ALT, alkaline phosphatase)
- Lymphocyte subset analysis (to include percentages and absolute numbers of CD3 T cells, CD4 T cells, CD8 T cells, B cells and NK cells); *N.B. this sample must be taken on the same day as the central lab samples below.*
- Peripheral blood samples for central labs:
 - 25ml in lithium heparin Viral and antigen-specific immunity & immune reconstitution
 - 10ml in EDTA chimerism analysis

The following samples should also be taken at days +100 and +360 post-stem cell transplant (+/- 10 days):

- Peripheral blood samples for central labs:
 - 10ml in EDTA TCR analysis

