16. TRIAL CLOSURE

16.1. End of Trial

For regulatory purposes the end of the trial will be when the final data item for the final patient is received by the UCL CTC (i.e. it is anticipated that this will be when the final patient completes their day 360 follow-up visit).. At this point the 'declaration of end of trial' form will be submitted to the Ethics Committee, as required.

Following this, UCL CTC will advise sites on the procedure for closing the trial at the site.

Once the end of trial has been declared, no more prospective patient data will be collected but sites must co-operate with any data queries regarding existing data to allow for analysis and publication of results.

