17.2.2. Analysis of secondary endpoints and secondary analyses

Incidence and severity of acute GvHD (whether dose-limiting or not)

Incidence and severity of acute GvHD (dose-limiting or not), as defined by the Glucksberg Scale, will be reported per dose level in frequency tables.

Incidence and severity of chronic GvHD

Incidence and severity of chronic GvHD will be reported per dose level in frequency tables.

Non-relapse mortality at 1 year

Non-relapse mortality (NRM) is defined as the time from registration to time of death without relapse. NRM will be presented using a Kaplan-Meier (KM) plot (grouped across dose level and per dose level), and 1-year NRM rate will be estimated (with 95% confidence intervals).

Overall- and Event-free survival at 1 year

Overall survival (OS) is defined as the time from registration to time of death from any cause. Event-free Survival (EFS) is defined as time from registration to the occurrence of any of the following events: graft failure, disease relapse, disease progression, or time of death from any cause. OS and EFS will be presented using KM plots (grouped across dose level and per dose level), and 1-year OS and EFS rates will be estimated (with 95% confidence intervals).

Incidence/type of infection requiring inpatient admission at 1 year

Infections that require inpatient admissions from date of Tem Infusion until +360 days post-stem cell transplant will be documented, and the type of infection and duration of inpatient stays will be reported per dose level.

Total Number of inpatient days at 1 year

The median and range for the total number of days that patients spend in hospital as inpatients from the date of Tem Infusion up to 1 year post allo-SCT will be reported.

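### One-year EFS is counted from registration while disease assessments are counted from transplant, so on the preferred schedule the one-year point falls before the nominal day +360 assessment and the rate is slightly too favourable

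*Protocol*

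**What the plan says.** Section 17.2.2 sets the time origin: "Event-free Survival (EFS) is defined as time from registration to the occurrence of any of the following events: graft failure, disease relapse, disease progression", or death from any cause. OS and NRM start at the same point. The section then says that "1-year OS and EFS rates will be estimated (with 95% confidence intervals".

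Registration comes before transplant. Section 7.1 states: "Registration will be undertaken centrally at UCL CTC and this must be performed prior to donor apheresis and patient transplant conditioning". Section 8.2.1 adds: "The preferred schedule is for donors to undergo apheresis between -14 to -7 days prior to day 0 of the stem cell transplant". It also permits later collection: "a maximum window for apheresis is allowed between -14 days prior to and up to +24 days following day 0 of the transplant".

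Disease is assessed on the transplant clock. Section 9.5 reads: "The following investigations should be performed at days +100, +180, +270 and +360 post-stem cell transplant (+/- 10 days"), and disease assessment is on that list. Section 9.6 ties annual status to the transplant date. Within 17.2.2 itself, inpatient infections are counted to day +360 after transplant and inpatient days to one year after transplant. For the end of the trial, section 16.1 says "it is anticipated that this will be when the final patient completes their day 360 follow-up visit".

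**The concern.** The protocol has two meanings of one year. For EFS, OS and NRM it ends a year after registration. For visits, annual follow-up, infections and inpatient days it ends about a year after transplant. Nothing reconciles them.

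This matters for EFS because relapse and progression can be found at a scheduled assessment and dated then. If the EFS year closes before the last assessment, what that assessment finds falls just outside the 1-year rate. For events found only at scheduled visits, the rate then mostly reflects disease status at about day +270. The error runs one way: EFS looks better than it is. Death dates do not depend on visits, so OS only has its horizon shifted and is not biased in this way. The two rates are reported together but are affected differently.

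**Working it through.** The protocol prints no expected EFS rate or relapse rate, so there is no figure of its own to reproduce. The first check is calendar arithmetic.

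**Inputs.** EFS origin: registration (17.2.2). Registration before apheresis and conditioning (7.1). Preferred apheresis: day -14 to -7; latest permitted: day +24 (8.2.1). Closing visit: day +360 ±10, that is days +350 to +370, 21 days (9.5). Maximum sample: 18 (17.1). Assumption: one year = 365 days.

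**Where the year ends.** If registration is r days before transplant, the EFS year ends on transplant day 365 - r.

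| Registration | Year ends | Closing-visit days after it | Nominal day +360 after it? |
|---|---|---|---|
| day -21 | +344 | 21/21 (100%) | yes |
| day -14 | +351 | 19/21 (90%) | yes |
| day -7 | +358 | 12/21 (57%) | yes |
| day -6 | +359 | 11/21 (52%) | yes |
| day -5 | +360 | 10/21 (48%) | no |
| day -1 | +364 | 6/21 (29%) | no |

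On the preferred schedule registration precedes an apheresis held on day -14 to -7. The year therefore ends at day +351 to +358 or earlier, always before the nominal visit. The last two rows can arise only if apheresis is late. Registration is then bounded only by the start of conditioning, whose length the protocol does not give.

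**Size, under assumptions not in the protocol.** Constant event hazard from day +28; 60% to 80% event-free over 365 days; visits uniform within ±10 days; a stated share of all EFS events dated at the next scheduled visit and the rest dated exactly. Overstatement = EFS read at day 365 - r minus true EFS at that day.

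- Share 25%: 0.7 to 1.3 points (registration day -7) and 0.9 to 1.8 points (day -14). In patients: 18 × 0.007 = 0.1 to 18 × 0.018 = 0.3.
- Share 50%: from 1.4 points (day -7, 80% event-free) to 0.673 - 0.637 = 3.6 points (day -14, 60% event-free). In patients: 18 × 0.014 = 0.3 to 18 × 0.036 = 0.6.
- Share 0%: nil.

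For scale, one patient in 18 is 1/18 = 5.6 points. With 13 of 18 event-free, the 95% Wilson interval is about 49% to 88%.

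**Check of possible remedies.**

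- *Transplant origin alone.* The year ends at day +365. The nominal visit and 16 of 21 window days (76%) fall inside; days +366 to +370 do not.
- *Infusion origin.* With infusion on day +24 to +32, the year ends at 24 + 365 = +389 to 32 + 365 = +397, past the final patient's expected last visit.
- *Kaplan-Meier curve read at day +370.* Event-free patients last seen on days +350 to +369 are censored before the reading point, while events found at the closing visit still count. The estimate comes out too low: about 0.65 against a true 0.72 in simulation (18 patients, half of events found at visits, everyone censored at the last visit).
- *Transplant origin with the closing visit placed at nominal day +360.* The estimate is about 0.722 against a true 0.721.

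**The case against.** The strongest reply concerns size. EFS includes death, which is dated when it happens, and graft failure and clinical relapse can surface between visits. A reader might infer an overstatement of up to 7 points. The same model gives that figure only if every EFS event is found at a scheduled visit, meaning nobody dies without a prior relapse. Section 2.1 points the other way: as general background it attributes deaths in about 10% of patients to GvHD and in a further 10-15% to the consequences of its prevention. That objection stands, and the smaller range above is the fair one.

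Two other strong readings also go too far. Late-found relapses are not lost: they remain on the Kaplan-Meier plots that 17.2.2 requires and miss only the 1-year point estimate. Nor is day +351 to +358 a ceiling for every patient, because apheresis is permitted up to day +24. With registration within about five days of transplant, most of the closing window falls inside the year.

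It can also be said that dating rules and visit windows belong in the SAP, which is not at hand. That is true of how a relapse is dated, and the bias does depend on relapses being dated when found. The time origin is different. The protocol fixes it, and in the same section it ends other 1-year endpoints on the transplant clock, so an SAP that follows the text inherits the mismatch.

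**Conclusion.** The mismatch is real and minor. On the preferred apheresis schedule the EFS year ends at transplant day +351 to +358 or earlier, before the nominal day +360 assessment and 57% to 90% or more of its window. One-year EFS is therefore biased upward for events first found at the closing visit.

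The direction follows from the text, provided such events are dated when found. The size rests on assumption: about 1 to 2 points if a quarter of events are found only at visits, about 1.4 to 3.6 if half are, and nothing for events dated between visits. That is usually well under one of 18 patients and small beside the sampling error.

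A reader might infer that dose finding is affected. It is not: the MTD rests on DLT estimates and the Safety Review Committee's recommendations (17.2.1), and EFS is a descriptive secondary endpoint with no comparator or threshold.

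**What to change.** In 17.2.2, start the EFS, OS and NRM clocks at stem cell transplant. Report the 1-year EFS rate at the day +360 assessment, counting every event first documented at or before that visit. Assign events found at that visit, and event-free patients last seen at it, to nominal day +360. Do not read the Kaplan-Meier curve at day +370, and do not count 365 days from Tem infusion.

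The cost is a sentence or two in 17.2.2, carried into the SAP, with no extra visits or data. The label becomes EFS at the day +360 post-transplant assessment, and the reported rate will be slightly less favourable.

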17. STATISTICS

17.1. Sample Size Calculation

The trial will be conducted as a dose-escalation study and use the Time-to-event Continual Reassessment Method (TITE-CRM; (17)) to guide dose-escalation decisions. The study aim is to identify the Maximum Tolerated Dose (MTD) and thus the Recommended Phase II Dose (RP2D) of Tem when given following allogenic stem cell transplantation. Four dose levels will be available for investigation $(1\times10^5/kg, 3\times10^5/kg, 1\times10^6/kg, 3\times10^6/kg)$. The MTD is defined as the largest dose of Tem that has an estimated risk of causing DLT (acute-pattern GvHD grade II-IV) equal or closest to 20% (the target toxicity level). We assume the relationship between DLT risk and Tem dose can be estimated using a two-parameter logistic model. Before the trial, we assume that the prior risk of DLT at the highest dose $(3\times10^6/kg)$ is 20%. We then use the prior calibration method of (18) to provide working prior beliefs for dose-toxicity risks at the other doses; this gives median DLT risks (and 90% credible intervals) shown in Table 1.

Dose	1x10⁵/kg	3x10⁵/kg	1x10 ⁶ /kg	3x10 ⁶ /kg
Prior median	8%	11%	15%	20%
90% Credible Interval	(0, 56)	(1, 63)	(1, 71)	(2, 78)

Table 1: Prior median probabilities of DLT risk per dose (90% credible interval). Model parameters (intercept and log-slope) from bivariate Normal distribution with means (-1.39, -1.17) and independent variances (2.60, 0.22) respectively.

A minimum of two patients will be treated at open dose cohorts. The first two patients will receive dose level 3 ($1x10^{6}$ /kg), and be followed for 72 days post infusion to monitor for GvHD onset. Data from patients 1 and 2 will be used to update the prior DLT risks, and a formal SRC meeting will be held to recommend the dose to be given to patients 3 and 4. After following up patients 3 and 4 for 72 days post infusion to monitor for GvHD onset, another formal SRC meeting will be held to recommend the dose to be given to patients 5 and 6. From then (after patient 5 and 6 begin treatment), partial follow-up data from the 72 day DLT window will be used to estimate DLT risks on an ongoing basis, so that new patients who are recruited before previous patients have completed follow-up may be entered onto the trial and receive Tem. Computations for updating the model will be performed in R Software(19).

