The maximum sample size for this study is 18 patients. This was chosen based on projected recruitment timelines for eligible patients, and obtaining sensible operating characteristics from the design. The trial may be terminated early if either i) Tem dose is escalated to dose level 4 without any DLTs occurring and 6 patients are dosed at dose level 4 without experiencing DLT – dose level 4 will be declared as the MTD (total of 8 patients), or ii) the chance that the risk of DLT at the lowest dose being above the target toxicity level is at least 90% – the trial will be stopped for safety.

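### One-year NRM, OS and EFS rates are promised with 95% confidence intervals in groups that may hold two to eight patients, where the usual Kaplan-Meier interval often collapses or under-covers; section 17.2.2 should call for counts or exact intervals

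*Protocol*

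**What the plan says.** Section 17.2.2 treats the three one-year outcomes alike. For non-relapse mortality: "NRM will be presented using a Kaplan-Meier (KM) plot (grouped across dose level and per dose level), and 1-year NRM rate will be estimated". The sentence goes on to attach a 95% interval to that rate. For overall and event-free survival, the Kaplan-Meier plots are "grouped across dose level and per dose level), and 1-year OS and EFS rates will be estimated (with 95% confidence intervals". The grouping phrase stands in the bracket that describes the plots. The clause on the rates repeats no grouping, and no interval formula is named.

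Section 17.1 fixes the group sizes:

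- "Four dose levels will be available for investigation" and "The maximum sample size for this study is 18 patients".
- "A minimum of two patients will be treated at open dose cohorts", and "The first two patients will receive dose level 3".
- The first early-stopping rule applies when there has been no DLT and "6 patients are dosed at dose level 4 without experiencing DLT". The section gives the total in that case as 8.

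**The concern.** The variance that normally accompanies a Kaplan-Meier estimate is Greenwood's. It is zero when nobody in the group has had the event, and the interval also degenerates when everybody has. In groups of two to eight patients the no-event outcome is common. A dose level with no deaths could then be tabulated as 0% NRM or 100% survival with an interval of no width, next to the recommended dose. At stake is how honestly the safety summary shows its uncertainty in a first study of this product.

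**Working it through.** **The plan's own figure.** Early-stopping rule (i): 2 patients at dose level 3 plus 6 at dose level 4 gives 2 + 6 = 8, as section 17.1 states. That path leaves one dose group of exactly two and a pooled group of eight.

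**Inputs.**
- Group sizes 2 and 6 (per dose), 8 (early stop) and 18 (maximum), from section 17.1.
- Event rate. The protocol gives no expected one-year rate. Section 2.1 cites about 10% deaths from GvHD and a further 10-15% mortality linked to delayed immune recovery, so I assume 20-25% (true S = 0.75 to 0.80) and add 10% (S = 0.90) as a low-rate case.
- No censoring before one year, also an assumption. It is reasonable for OS and EFS because section 3 plans at least one year of follow-up after transplant.

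**Formulas.** Without censoring, the Kaplan-Meier estimate at one year with d events in n patients is 1 − d/n, and Greenwood's variance is S(1−S)/n evaluated at the estimate. The probability of a degenerate interval is Sⁿ + (1−S)ⁿ. Coverage is the sum of the binomial probabilities of those d whose interval contains the true S. An undefined log-log interval counts as not covering.

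**Degenerate intervals.**
- n = 2: 0.75² + 0.25² = 0.625; 0.80² + 0.20² = 0.680.
- n = 8: 0.75⁸ = 0.100; 0.80⁸ = 0.168 (the all-events term is negligible).
- n = 18: 0.75¹⁸ = 0.006; 0.80¹⁸ = 0.018; 0.90¹⁸ = 0.150.

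| n | Event rate | Degenerate | Coverage: plain / log / log-log |
|---|---|---|---|
| 2 | 25% | 63% | 38% / 38% / 38% |
| 2 | 20% | 68% | 32% / 32% / 32% |
| 6 | 25% | 18% | 78% / 82% / 78% |
| 6 | 20% | 26% | 72% / 74% / 72% |
| 8 | 25% | 10% | 87% / 90% / 87% |
| 8 | 20% | 17% | 82% / 83% / 78% |
| 8 | 10% | 43% | 56% / 57% / 53% |
| 18 | 25% | 0.6% | 94% / 86% / 94% |
| 18 | 20% | 1.8% | 88% / 90% / 93% |
| 18 | 10% | 15% | 84% / 85% / 82% |

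Most of the shortfall at n = 2 to 8 comes from the no-event outcome itself. At n = 8 and a 20% event rate, for example, plain coverage among non-degenerate samples is 0.822/0.832 = 99%.

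**Exact interval for comparison.** In the rows above, Clopper-Pearson coverage is at least 96.6%, and its width is never zero. With no events, its lower limit for survival is 0.025^(1/n): 16% at n = 2, 54% at n = 6, 63% at n = 8 and 81% at n = 18. The matching upper limits for the event rate are 84%, 46%, 37% and 19%. For 1 event in 8, the survival intervals are 67-100% (log), 39-98% (log-log) and 47-99.7% (exact).

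**The case against.** The strongest reply is that the protocol does not commit to the faulty interval. A reader might infer that section 17.2.2 promises confidence intervals for each dose level. The wording does not establish that: the per-dose phrase belongs to the plots, and rates given only for the pooled group fit the text equally well. A reader might also infer that no later analysis plan could repair the matter. That is true only of switching between transformations of the Greenwood interval. Nothing in the protocol prevents an exact or zero-event-valid interval, and the choice of method is ordinarily left to the analysis plan, which is not at hand. Both points stand, and they make the concern conditional on the usual method being used.

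Three further points stand:

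- With one event in eight, log-log is not too short on the lower side; its lower limit (39%) lies below the exact one (47%).
- A log-log interval with no events is missing rather than falsely narrow.
- For NRM, a Kaplan-Meier analysis would presumably censor at relapse. The binomial calculation therefore describes it exactly only if nobody relapses.

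The objection does not remove the problem on the pooled-only reading. At the protocol's own total of eight, the usual intervals cover 78-90% at a 20-25% event rate.

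**Conclusion.** The point holds in a limited form. If the usual Greenwood-based intervals are used, they are degenerate in 63-68% of two-patient groups and in 10-17% of eight-patient groups. Coverage with eight patients is 78-90%. At the full 18 patients and 20-25% event rates the difficulty is small: 0.6-1.8% degenerate, with log-log coverage of 93-94%. It returns if events are rare: at a 10% rate, 15% are degenerate and coverage is 82-85%.

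These figures rest on assumed event rates and on no censoring before one year. The 20-25% comes from general transplant background with no stated one-year horizon, and patients who reach infusion are selected.

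A reader might infer that the MTD or recommended Phase II dose would be distorted. The document does not support this: section 17.2.1 bases both on the DLT model estimates and the Safety Review Committee's recommendations. What is affected is the honesty of a descriptive secondary summary. The change is worth making because it is cheap and the alternative is plainly better in groups this small.

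**What to change.** Amend section 17.2.2 and carry the wording into the analysis plan:

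- **Per dose level:** report one-year outcomes as events/N, with an exact (Clopper-Pearson) 95% interval, or as counts only in groups of about two. There an exact interval is valid but says almost nothing (16-100% survival for 0 of 2).
- **Pooled OS and EFS:** give an exact 95% interval. If anyone is censored before one year, use a Kaplan-Meier interval that stays valid with zero events, such as the beta product procedure.
- **NRM:** state that events/N counts relapse as a competing event rather than censoring it, since this is a different quantity from one minus Kaplan-Meier.

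Per-dose Kaplan-Meier curves may stay as a display choice. The cost is a few lines of text, with no effect on sample size, conduct or dosing. The downside is wider, less favourable intervals.
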